7.2.1 Screening

After written informed consent has been obtained, subjects will be screened in order to assess eligibility for study participation. All screening procedures must be performed within 14 days prior to start of IP administration, unless otherwise noted.

Subjects who meet the inclusion and exclusion criteria will be eligible to be enrolled in the study.

Laboratory assessments used to determine subject eligibility may be repeated once for confirmation (up to a total of 2 times during the 14-day screening period) if necessary before the subject is considered a screen failure. If any out of range assessments are repeated during the screening period, the value that is closest to the enrollment date will apply for the determination of eligibility.

A subject may be rescreened up to 3 additional times during the study at the discretion of the investigator. The subject must be re-consented if a re-screening attempt occurs outside the 14-day screening period. Hepatitis serology does not need to be repeated in

Approved

case of re-screening, or for eligibility, if it was performed within 6 weeks prior to start of treatment with AMG 673.

Subjects who do not meet the eligibility criteria within the 14-day screening period will not be eligible for enrollment. Subjects who are deemed ineligible will be documented as screen failures.

The following procedures are to be completed during the screening period at the time points designated in the Schedules of Assessments ([Table 6](#)). Assessments that were performed as standard of care prior to signature of informed consent but within 14 days prior to start of treatment with AMG 673 can be used as screening assessments and do not need to be repeated to confirm subject eligibility.

- Confirmation that the ICF has been signed
- Demographic data including sex, age, race, and ethnicity will be collected in order to study their possible association with subject safety
- Clinical evaluation
 - Physical examination as per standard of care (including medical/surgical history). Physical examination findings should be recorded on the appropriate eCRF.
 - ECOG performance status
 - Height and weight
- Vital signs (ie, blood pressure, heart rate, respiratory rate, temperature)
- Pulse oximetry
- ECG triplicate measurement
- Laboratory assessments: hematology, chemistry, coagulation, urinalysis, serum pregnancy test (females only), and hepatitis serology
- Bone marrow aspirate and biopsy
- Serious adverse event reporting
- Documentation of concomitant and rescue medications.

7.2.2 Treatment

Treatment begins on day 1 (cycle 1 day 1) when the first IV infusion of investigational product is administered to a subject.

In addition to the mandatory hospitalization period (see [section 6.2.1.1](#)), there will be at least twice weekly visits to the site during the treatment period. Weekly visits will apply during the infusion-free interval between 2 treatment cycles.

The following procedures will be completed during the treatment period at the times designated in the Schedules of Assessments ([Section 7.1](#)).

The results of the D1 laboratory tests taken prior to infusion start will not have to be available before starting treatment with AMG 673. Laboratory assessments that were done within 24 hours prior to treatment start do not need to be repeated at D1 prior to infusion.

- Hospitalization (see [section 6.2.1.1](#) for minimum required hospitalization times)
- investigational product infusions (See [Section 6.2.1.1](#) for details)
- Clinical evaluation
 - Physical examination as per standard of care. Physical examination findings should be recorded on the appropriate eCRF
 - ECOG performance status
 - Weight
- Vital signs (ie, blood pressure, heart rate, respiratory rate, and temperature)
- Pulse oximetry
- ECG triplicate measurement
- Laboratory assessments: hematology, chemistry, coagulation, urinalysis, and serum pregnancy test (females only)
- 
- AMG 673 PK sample collection
-  sample collection
- Bone marrow aspirate / biopsy
- Serious adverse event reporting
- Adverse event reporting
- Disease-related event reporting
- Documentation of concomitant and rescue medications
- CT scan or MRI (to be considered in case of CNS adverse event of grade ≥ 3 only, particularly in cases of confusion, disorientation or seizures)
- Receipt of protocol-required therapies
- For subjects to whom intra-subject dose escalation (see [Section 3.1](#)) applies:
 - ECG assessments should be performed as in cycle 1, regardless of actual study cycle
 - PK samples should be taken as in cycles 1 and 2, respectively, regardless of actual study cycle
 - All other assessments should be performed as per the schedule of assessments for the actual cycle.

Approved

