4.2 Exclusion Criteria

201. Active extramedullary AML in the central nervous system (CNS).
202. Known hypersensitivity to immunoglobulins.
203. White blood cells (WBC) $>$ 15,000 cells/mcL (15 cells \times 10⁹/L) at screening. In subjects with WBC $>$ 15,000 cells/mcL at screening with lymphocyte predominance, subject may be deemed eligible for the trial by the Amgen physician, after discussion with the investigator.
204. Prior malignancy (other than in situ cancer) unless treated with curative intent and without evidence of disease for $>$ 2 years before screening.
205. Autologous HSCT within 6 weeks prior to start of AMG 673 treatment.
206. Allogeneic HSCT within 3 months prior to start of AMG 673 treatment.
207. Non-mangeable graft versus host disease.
208. History or evidence of cardiovascular risk including any of the following:
 - History or evidence of clinically significant arrhythmias (ventricular fibrillation, ventricular tachycardia, supraventricular tachycardia, atrial tachycardia/flutter, atrial fibrillation with rapid ventricular response, second or third degree atrioventricular block, and sick sinus syndrome).
 - Exception: Subjects with controlled atrial fibrillation for $>$ 30 days prior to study day 1 are eligible. Controlled atrial fibrillation is defined as atrial fibrillation with no rapid ventricular response which requires no change in medication/dosage or addition of new medication or hospital admission within 30 days prior to study day 1.

- History of acute coronary syndromes (eg, myocardial infarction and unstable angina) and/or coronary angioplasty within 6 months prior to study day 1.
 - History or evidence of \geq Class II congestive heart failure as defined by New York Heart Association (NYHA).
 - Chronic hypertension (defined as a systolic blood pressure [SBP] >140 mm Hg and/or diastolic blood pressure [DBP] >90 mm Hg which cannot be controlled by anti-hypertensive therapy).
 - Subjects with intra-cardiac defibrillators.
 - Abnormal cardiac valve morphology (\geq grade 2) (subjects with grade 1 abnormalities [ie, mild regurgitation/stenosis] can be entered on study. Subjects with moderate valvular thickening should not be entered on study).
209. History of arterial thrombosis (eg, stroke or transient ischemic attack) in the past 3 months.
210. Active infection requiring intravenous antibiotics within 1 week of study enrollment (day 1).
211. Known positive test for human immunodeficiency virus (HIV).

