6.3 Other Protocol-required Therapies

All other protocol-required and recommended therapies including corticosteroids, that are commercially available are not provided or reimbursed by Amgen (except if required by local regulation). The investigator will be responsible for obtaining supplies of these therapies.

Oxygen: Oxygen administration as a supportive measure is permitted during study treatment.

Hydroxyurea: Hydroxyurea for 7 days at a dose of 1 – 10 g / day is permitted prior to the first cycle of IP treatment for subjects with high WBC (> 15,000 cells/mcL or 15 cells x 10⁹/L). Administration of hydroxyurea after the start of IP must be approved and discussed with the Amgen medical monitor.

Dexamethasone: Premedication with dexamethasone is required prior to day 1 and day 5 of AMG 673 dosing and prior to each step-up dose of AMG 673 to mitigate the risk of CRS in Schedule A. For Schedule B, premedication with dexamethasone is required prior to a dose administered on day 1 and each step-up dose in cycle 1, and prior to every dose in subsequent cycles. When dosed, dexamethasone should be administered as a single IV dose (8 mg) within 1 hour of start of infusion.

Tocilizumab: Tocilizumab may be added to CRS treatment regimen or required to be used in combination with dexamethasone to treat CRS as per protocol [Section 6.6](#).

For administration of tocilizumab or dexamethasone and tocilizumab after occurrence of CRS, follow guidance in [Section 6.6](#). Additional details regarding these protocol-required therapies are provided in the IPIM.

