- The Amgen medical monitor must be consulted prior to re-starting treatment
- If CRS occurred during AMG 673 infusion, infusion has been interrupted for at least 72 hours
- The event has resolved to grade ≤ 1 prior to re-starting treatment

AMG 673 therapy should be restarted 1 dose level below the dose at which the event occurred. If this lower dose level is well tolerated (ie, absence of grade ≥ 3 CRS), then a dose step up to the subject's target dose level can occur. An intermediate dose may be administered after consultation with the Amgen medical monitor prior to stepping up to the target dose.

Please also refer to the general guidance for re-start of treatment after adverse events in [Section 6.2.1.4](#)

For Grade 3 and 4 CRS, please see [Section 2](#) for DLT considerations.

Tumor Lysis Syndrome

Subjects with AML and WBC $<10,000/\text{mcl}$ or $10 \text{ cells} \times 10^9/\text{L}$ are considered to be at low risk for tumor lysis syndrome. WBC $>10,000/\text{mcl}$ and $<50,000/\text{mcl}$ are considered to be at intermediate risk, and subjects with WBC $>50,000/\text{mcl}$ are considered at high risk. This protocol requires that subjects have a maximum WBC count of $15,000/\text{mcl}$ or $15 \text{ cells} \times 10^9/\text{L}$.

Additional high-risk features include baseline uric acid $>450 \text{ mcg/L}$ (7.5 mg/dl), serum creatinine $> 1.4 \text{ mg/dL}$, and lactate dehydrogenase (LDH) greater than the ULN.

Patients with intermediate risk WBC count and elevated baseline uric acid ($> 450 \text{ mcg/L}$), serum creatinine $>1.4 \text{ mg/dl}$, or LDH greater than ULN will be recommended to receive allopurinol prophylaxis. Typical dosing is 600-800 mg/day administered BID or QID and should begin 3 days before the first dose of study drug. Patients should be well hydrated and supplemented with intravenous fluid as clinically indicated.

For grade 3 and 4 tumor lysis syndrome, please see [Section 6.2.1.3](#) for DLT considerations.

Infection Prophylaxis

Subjects who may experience neutropenia for 7 days or longer are at a high risk for infectious complications. As appropriate, these subjects should be administered prophylactic antibacterial (eg, fluoroquinolones), antifungal and antiviral medications. These subjects should be monitored for early signs of breakthrough infections after the initiation of antibacterial therapy to prompt additional evaluation and possible therapy modification.

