A serum pregnancy test will be performed locally at each site on all females unless they are surgically sterile or > 2 years postmenopausal. On visits where required, the serum pregnancy test must be performed prior to dosing with investigational product. If the pregnancy test is positive at day 1 of cycle 1, the subject should not be given investigational product.

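### Protocol Section 7.2.2 lets the first infusion start before day-1 laboratory results are known, so the day-1 pregnancy stop in Section 7.3.9 may be unable to operate

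*Protocol*

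**What the plan says.** Three parts of the protocol bear on the pregnancy test.

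- **Section 7.2.2 (Treatment)** says: "The results of the D1 laboratory tests taken prior to infusion start will not have to be available before starting treatment with AMG 673". It adds: "Laboratory assessments that were done within 24 hours prior to treatment start do not need to be repeated at D1 prior to infusion". The procedures listed below these sentences include "Laboratory assessments: hematology, chemistry, coagulation, urinalysis, and serum pregnancy test (females only").
- **Section 7.3.9 (Clinical Laboratory Tests)** says that, at visits where it is required, "the serum pregnancy test must be performed prior to dosing with investigational product". It continues: "If the pregnancy test is positive at day 1 of cycle 1, the subject should not be given investigational product".
- **The schedules of assessments for cycle 1 (Tables 6, 9 and 12)** place the serum pregnancy test at screening and again before the dose on day 1.

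On the white blood cell (WBC) count, Section 6.6 says: "This protocol requires that subjects have a maximum WBC count of" 15,000/mcl, and gives no time point. Exclusion 203 in Section 4.2 sets the same limit at screening. For a count above it with lymphocyte predominance, it adds that the "subject may be deemed eligible for the trial by the Amgen physician, after discussion with the investigator".

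**The concern.** A stopping rule that depends on a test result works only if the result is read before the action it is meant to stop. Section 7.3.9 makes the cycle 1 day 1 pregnancy result a bar to dosing. Section 7.2.2 tells the same site, about the same day's samples, that it may dose without seeing results. If the site relies on 7.2.2, the pre-dose test on day 1 is still drawn but no longer protects the first infusion.

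What is at stake is exposure of a pregnant subject to a first-in-human product. The protocol treats pregnancy as serious throughout: a positive test excludes (criterion 223), pregnancy on study ends treatment permanently (Section 6.2.1.4), and pregnancies are reportable through 15 weeks after the last dose (Section 9.3). This is a point about subject protection and consistent instructions, not about an estimate or an error rate.

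**Working it through.** No arithmetic applies, since the plan states no figure on this point. The check is a comparison of texts.

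1. **Do the two rules cover the same event?** Yes. Section 7.2.2 defines the start of treatment as the first infusion on cycle 1 day 1, and its waiver concerns samples taken that day before the infusion. The bar in 7.3.9 concerns the test at day 1 of cycle 1.

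2. **Does the waiver cover the pregnancy test?** As written, yes. It refers to the D1 laboratory tests without exception, and 7.2.2 groups the serum pregnancy test with hematology, chemistry, coagulation and urinalysis as laboratory assessments.

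3. **Does the timing sentence in 7.3.9 close the gap?** No. It requires the test to be performed before dosing. A sample can be drawn and sent before the infusion and reported after it.

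4. **Does the 24-hour substitution close the gap?** Only in one case. It removes the need for a repeat test; it does not say that the earlier result must be known. If the test within 24 hours is itself the screening test, Section 5 requires screening results to show that all criteria are met before enrollment, so that result would be known. A separate test in that window carries no such requirement.

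5. **What protection remains if the day-1 result is unread?** The screening test, exclusion 223 (positive test) and exclusion 221 (highly effective contraception). Section 7.2.1 and the schedules set the screening window at 14 days, so the last known pregnancy result can be up to 14 days old at the first infusion. The cycle 1 schedules place no other pregnancy test between screening and the pre-dose sample on day 1.

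6. **WBC count, for comparison.** Exclusion 203 is decided at screening, and Section 5 makes screening results a condition of enrollment. No section makes a day-1 WBC value a reason to withhold the infusion. The 7.2.2 waiver therefore has no day-1 WBC rule to contradict. The mismatch lies between 6.6 and 203: the former gives no time point and does not mention the lymphocyte-predominance exception.

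**The case against.** The strongest reply is that 7.2.2 is permissive and 7.3.9 is a specific prohibition. A site that waits for the pregnancy result satisfies both, and a careful investigator would read the specific rule as governing. That is fair, and it means the texts are not impossible to obey together. But nothing in 7.2.2 points to 7.3.9 or carves out the pregnancy test, so a site acting exactly as 7.2.2 permits can make the stop unworkable. The defect is the missing exception.

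The second reply is that the residual risk is small: a screening test within 14 days, required contraception and an explicit exclusion. This limits the likely consequence. It does not explain why a second test is scheduled before the dose if its result need not be seen.

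A reader might also be tempted by a stronger reading, that 7.2.2 equally defeats the WBC limit. The documents do not support it:

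- The limit in exclusion 203 is a screening criterion, and there is no day-1 WBC stop to defeat.
- Section 6.3 says that hydroxyurea "is permitted prior to the first cycle of IP treatment for subjects with high WBC". This largely fits the criterion: exclusion 215 allows hydroxyurea for count control until treatment starts, and Section 7.2.1 lets an out-of-range value be repeated, with the value closest to enrollment deciding.
- Projecting how far a count could rise between screening and day 1 would need a doubling time, which the documents do not give.
- An argument that high counts would distort the dose-limiting toxicity (DLT) rate and the maximum tolerated dose goes further than the text. Under Section 6.2.1.3, grade 3 tumor lysis that is managed and resolves within 7 days without end-organ damage is not a DLT, and grade 2 or 3 cytokine release syndrome counts only under listed conditions.

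**Conclusion.** The inconsistency between Sections 7.2.2 and 7.3.9 is real. As written, the waiver on day-1 results reaches the pregnancy test, and neither the requirement to perform the test before dosing nor the 24-hour substitution makes the result a precondition of the infusion in general. The day-1 stop can then be bypassed by a site acting within 7.2.2.

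The size is bounded in time but not in frequency. The last known result may be up to 14 days old. The documents do not give the number of subjects of childbearing potential or any pregnancy rate, so no probability is offered. The conclusion assumes that 7.2.2 means what it says for every test it lists; if the sponsor intended an unstated exception, the correction is one of wording only.

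On WBC, only a minor ambiguity stands: the maximum in Section 6.6 has no time point and omits the exception that exclusion 203 allows. It is not evidence that the limit goes unenforced where the protocol places it.

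**What to change.** Reconcile Section 7.2.2 with Section 7.3.9 so that the permission to start before day-1 results are available does not contradict the cycle 1 day 1 pregnancy stop. The same edit should say how the stop applies when a test from the preceding 24 hours replaces the day-1 sample. How the two sections are aligned is the sponsor's decision.

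The cost is a sentence or two in an amendment. The test is already scheduled before the dose in Tables 6, 9 and 12 and run at local laboratories (Sections 7.2 and 7.3.9), so if the stop is kept as it stands, the operational burden is at most a short wait for one result.

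In the same amendment, bring the WBC sentence in Section 6.6 into line with exclusion 203 on the time point and the lymphocyte-predominance exception. No day-1 WBC rule is proposed here.

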7.2.3 End of Treatment Visit

The EOT visit will occur at the end of the last treatment cycle. For subjects who prematurely discontinue IP treatment, the EOT visit should occur as soon as possible after the last dose of investigational product was administered. The following procedures will be completed during the EOT visit as designated in the Schedules of Assessments ([Section 7.1](#))

- Clinical evaluation
 - Physical examination as per standard of care. Physical examination findings should be recorded on the appropriate eCRF.
 - ECOG performance status
 - Weight
- Vital signs (ie, blood pressure, heart rate, respiratory rate, and temperature)
- Pulse oximetry
- Laboratory assessments: hematology, chemistry, coagulation, urinalysis
- [REDACTED]
- AMG 673 PK sample collection
- [REDACTED] sample collection
- Serious adverse event reporting
- Adverse event reporting
- Disease-related event reporting
- Documentation of concomitant and rescue medications

7.2.4 End of Study Visit

The EOS visit is a safety follow-up visit that is to be performed at least 4 weeks (or up to 7 days thereafter) after the last dose of AMG 673 or prior to the initiation of other AML therapy whichever occurs earlier. All efforts should be made to conduct this visit. If it is not possible to conduct the EOS visit, documentation of the efforts to complete the visit should be provided in the source documents and noted as not done in the eCRF.

Subjects who complete the EOS visit will be considered to have completed the study.

The following procedures will be completed at the EOS visit as designated in the Schedules of Assessments ([Section 7.1](#))

Approved

- Clinical evaluation
 - Physical examination as per standard of care. Physical examination findings should be recorded on the appropriate eCRF.
 - ECOG Performance Status
 - Weight
- Vital signs (ie, blood pressure, heart rate, respiratory rate, and temperature)
- Pulse oximetry
- ECG triplicate measurement
- Laboratory assessments: hematology, chemistry, coagulation, urinalysis
- [REDACTED]
- Bone marrow aspirate / biopsy
- AMG 673 PK sample collection
- [REDACTED] sample collection
- Serious adverse event reporting
- Adverse event reporting
- Disease-related event reporting
- Documentation of concomitant and rescue medications

7.3 Description of Study Procedures

The sections below provide a description of the individual study procedures listed in [Section 7.2](#)

7.3.1 Informed Consent

A signed ICF must be obtained from each subject prior to any study-mandated procedures.

7.3.2 Demographic Data

Demographic data collection including sex, age, race, and ethnicity will be collected in order to study their possible association with subject safety and treatment effectiveness. Additionally, demographic data will be used to study the impact of the protocol-required therapy on biomarker variability and PK.

7.3.3 Medical History and Prior Therapy

The investigator or designee will collect a complete medical and surgical history that started 5 years prior to screening through prior to first dose of AMG 673. Medical history will include information on the subject's concurrent medical conditions. Record all findings on the medical history eCRF.

Approved

Relevant medical history, including antecedent hematologic or oncologic disease, other diseases/symptoms such as fatigue, bleeding, and infection (resolved and ongoing) will be collected. AML history must date back to the initial diagnosis and any response duration must be recorded. The current toxicity grade will be collected for each condition that has not resolved.

Exception: No toxicity grade should be recorded for ongoing AML history.

All prior cancer treatment therapies will be collected.

7.3.4 Concomitant Medications

Concomitant therapies are to be collected from informed consent through the EOS. In case the screening period is shorter than 2 weeks (ie, informed consent is obtained less than 2 weeks prior to start of study treatment), concomitant medications for which washout periods have to be observed (refer to [section 6.9](#)) are to be collected starting 2 weeks prior to start of study treatment. Collect therapy name, indication, dose, unit, frequency, route, start date, and stop date.

